15.1.2. Adverse Reaction

An adverse drug reaction (ADR) is defined as all untoward and unintended responses to an IMP related to any dose administered. The definition implies a reasonable possibility of a causal relationship between the event and the IMP i.e. there are facts (evidence) or arguments to suggest a causal relationship.

15.1.3. Serious Adverse Event

An SAE as defined by the International Council for Harmonisation of Technical Requirements for Pharmaceuticals for Human Use (ICH) is any untoward medical occurrence that meets any of the following conditions:

- Results in death
- Is life-threatening (i.e. the patient was at risk of death at the time of the event; it does not refer to an event which hypothetically might have caused death if it were more severe)
- Requires in-patient hospitalization or prolongation of existing hospitalization

- Results in persistent or significant disability/incapacity
- Results in a congenital anomaly/birth defect

Important medical events that may not be immediately life-threatening or result in death or hospitalization but may jeopardize the patient or may require intervention to prevent one of the other outcomes listed in the definition above, should also be considered serious.

15.2. Monitoring and Reporting Events

15.2.1. Adverse Events

Any AE experienced by a patient between signing the informed consent form (ICF) and 28 days after the last administration of bemcentinib is to be recorded in the eCRF regardless of the severity and causality of the event, although only events considered to be related to treatment need to be recorded between the last administration of bemcentinib and the end of the 28-day follow up period. If bemcentinib-related toxicities continue beyond the Follow-up period, patients will be followed until all bemcentinib-related toxicities have resolved to Grade ≤1, stabilized or returned to baseline.

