9.3.4. Follow Up

An AE will be monitored for 28 days after the last dose of bemcentinib although only events considered to be related to treatment need to be recorded in the eCRF between the last administration of bemcentinib and the end of the 28 day follow up period. If bemcentinib-related toxicities continue beyond the follow up period, patients will be followed until all bemcentinib-related toxicities have resolved to <Grade 1, stabilized or returned to baseline. If necessary, follow up monitoring for AEs may be conducted over the telephone.

SAEs with a suspected relationship to bemcentinib will be collected beyond the 28-day follow-up period until the event is resolved to \leq Grade 1, stabilized or returned to baseline.

All patients that have permanently discontinued study treatment for whatever reason must be followed for survival. The investigator or designee must confirm with the patient at the time of the Final Study Visit how the patient will be followed for survival (e.g. contact with family or

health care provider). Survival follow-up must be conducted at least every 3 months by the investigator or designee and the date-of-death reported in the eCRF.

All subsequent anticancer therapy for AML or MDS must be reported in the eCRF.

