15.2.2. Serious Adverse Events

Any SAE experienced by a patient between the time of the first administration of bemcentinib and 28 days after the last administration is to be recorded on an SAE Report Form as well as in the eCRF within 24 hours of knowledge by the investigator of its occurrence, regardless of the severity and causality of the event. The exception to this will be patients who experience an SAE due to a Screening assessment. Such events should also be reported and will be recorded in the CSR. SAEs with a suspected relationship with bemcentinib will be collected indefinitely. The SAE Report Form should be e-mailed to the [Syneos](mailto:[contact]) Health Safety and Pharmacovigilance Global Safety Mailbox [contact].

All SAEs that have not resolved by the end of the study, or that have not resolved upon the patient's discontinuation from the study, must be followed until any of the following occur:

- The event resolves
- The event stabilizes
- The event returns to baseline status
- The event can be attributed to agents other than the IMP or to factors unrelated to study conduct
- It becomes unlikely that any additional information can be obtained

Any event requiring hospitalization (or prolongation of hospitalization) that occurs during the course of a patient's participation in a clinical study must be reported as an SAE. Exclusions to this are hospitalizations:

- For pre-scheduled or routine elective procedures (as long as the qualifying condition did not worsen or progress, in the opinion of the investigator, since signing the ICF)
- For social reasons, in the absence of an AE e.g. for respite care
- Due to expected deterioration caused by disease progression

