15.4. Investigator's Safety Responsibilities

The investigator's responsibilities include the following:

- Monitor and record all AEs, including SAEs, regardless of the severity or relationship to bemcentinib
- Determine the seriousness, relationship and severity of each event
- Determine the onset and resolution of each event
- Complete an SAE form for each SAE as outlined in Section 15.2.2
- Pursue SAE follow-up information actively and persistently
- Ensure all AE and SAE reports are supported by documentation in the patient medical records
- Report SAEs to their local REC/IRB, as required by local law

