#### 4.3.4 Follow Up

An AE will be monitored for 28 days after the last dose of BGB324, although only events considered to be related to treatment need to be recorded in the electronic Case Report Form (eCRF) between the last administration of BGB324 and the end of the 28 day follow up period. If BGB324-related toxicities continue beyond the follow up period, patients will be followed until all BGB324-related toxicities have resolved to  $\leq$ Grade 1, stabilised or returned to baseline. If necessary, follow up monitoring for AEs may be conducted over the telephone.

SAEs with a suspected relationship to BGB324 will be collected beyond the 28-day follow-up period until the event is resolved to  $\leq$  Grade 1, stabilized or returned to baseline.

All patients that have permanently discontinued study treatment for whatever reason must be followed for survival. The investigator or designee must confirm with the patient at the time of the Final Study Visit how the patient will be followed for survival (e.g. contact with family or health care provider). Survival follow-up must be conducted at least every 3 months by the investigator or designee and the date-of-death reported in the eCRF.

All subsequent anticancer therapy for AML or MDS must be reported in the eCRF.

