## 5 Statistical Methodology

### 5.1 Planned Analyses

Disposition analyses will be carried out using the Enrolled Population. Demographic and baseline characteristics analyses will be carried out using the Safety Analysis Set. Safety analyses will be carried out using the Safety Analysis Set. Efficacy analyses will be carried out using the Efficacy Analysis Population.

Summary statistics will be presented for continuous variables, by way of n, mean, standard deviation (SD), median, minimum (Min) and maximum (Max) and by way of group frequencies and percentages for categories of categorical variables. No statistical comparison of dose levels or treatment groups will be performed. Percentages will be calculated using the total patients per dose cohort in the given population unless otherwise noted.

All data from this study will be presented in data listings. All listings will be sorted by dose level or treatment group and patient.

Baseline will be defined as the last assessment prior to study drug administration. Typically this will be Cycle 1 Day 1. Where calculated, absolute change from baseline will be presented using the following formula for each parameter: Value at the visit/timepoint – value at baseline.

Data will be presented by dose/cohort and overall in Part A and by treatment group (AML (B1: BGB324 400/200 mg Single agent; B2: BGB324 400/200 mg + Cytarabine; B3: BGB324 400/200 mg + Decitabine; B5: BGB324 400/200 mg + Cytarabine) and MDS (B4: BGB324 400/200 mg) ) and overall in Part B.

Where appropriate, the data for patients who received the MTD during Part A will be combined with that for patients who received the MTD in Part B for the purpose of data summarisation. A clear distinction will be made in the relevant Tables to differentiate between the cohort who received the MTD during the dose escalation phase of Part A, the MTD cohort from the cohort expansion phase in Part A, and the combined MTD cohort.

Any patient treated with bemcentinib beyond disease progression will be followed for the same safety and efficacy assessments as for all other patients enrolled into the study. The data for patients treated beyond progression will be presented in both a combined output (with all patients) and a separate output (reflecting a new period of analysis with the data collected in this period). All data collected will be included in the study CSR and may be presented at congress/symposia.

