### 5.8.1 Adverse events

The number and percentage of patients reporting TEAEs will be tabulated by MedDRA preferred term and system organ class, and summarized by CTCAE grade also. All AEs commencing prior to dosing with study medication will be excluded from the tabulation but will be fully listed.

A subject with more than one occurrence of the same adverse event in a particular system organ class will be counted only once in the total of those experiencing adverse events in that particular system organ class. If a subject experiences the same adverse event at more than one severity, or with more than one relationship to study drug, the most severe rating or the stronger causal relationship to study drug will be given precedence. Any missing severity, causality, or outcome will not be imputed and classed as unknown.

An overall summary classifying subjects with events according to seriousness, severity, maximum relationship to BGB324, and maximum CTCAE grade will also be presented.

Related events are defined as events that are definitely, possibly or probably related to study medication or with an unknown relationship.

Treatment-Emergent AEs are any AEs that start or worsen after first dose of study drug until 28 days following the last dose. AEs with partial onset dates will be assumed to have the latest possible onset date (while accounting for stop date) for determining treatment emergence, but no formal imputation will be done. AEs that have missing onset dates will be considered to be treatment-emergent, unless the stop date is known to be prior to the first administration of BGB324.

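### The SAP counts AEs of any cause to 28 days after the last dose, but after the last bemcentinib dose only related AEs and SAEs must be recorded, so unrelated non-serious AEs can be under-counted

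*Protocol*

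**What the plan says.** **Collection.** Protocol 15.2.1 opens by requiring that any AE from consent to 28 days after the last bemcentinib dose "is to be recorded in the eCRF regardless of the severity and causality of the event". The same sentence then adds that "only events considered to be related to treatment need to be recorded between the last administration of bemcentinib and the end" of the 28-day period. Protocol 9.3.4 has the same limit: "only events considered to be related to treatment need to be recorded in the eCRF between the last administration of bemcentinib". SAP 4.3.4 carries it over: "only events considered to be related to treatment need to be recorded in the electronic Case Report Form (eCRF").

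Two other protocol texts bear on the same period. Section 15.2.2 keeps serious events outside the limit: "Any SAE experienced by a patient between the time of the first administration of bemcentinib and 28 days after the last administration" goes on the SAE form and in the eCRF whatever its causality. Section 15.4 lists among the investigator's general duties: "Monitor and record all AEs, including SAEs, regardless of the severity or relationship to bemcentinib". It names no time window.

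**Analysis.** SAP 5.8.1 says: "Treatment-Emergent AEs are any AEs that start or worsen after first dose of study drug until 28 days following the last dose". There is no causality condition. On that definition the SAP plans tables of all AEs, AEs by grade, non-serious AEs, AEs of Grade 3 or higher, and preferred terms reaching 10% of patients. On denominators, SAP 5.1 says: "Percentages will be calculated using the total patients per dose cohort in the given population unless otherwise noted". SAP 5.14, which lists changes from the protocol, does not mention the difference between the collection rule and the TEAE window.

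**The concern.** Safety and tolerability is the primary objective of Part B, and the TEAE tables are its main display. If the analysis window is wider than the collection rule, part of each all-cause table rests on events that sites were not obliged to enter. Whether an event is entered then depends on a causality judgement made by an investigator in an open-label study. SAP 5.12 treats missing data as missing at random and replaces nothing, but events left out because they were judged unrelated are not missing at random.

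The protocol also points both ways. A site that follows the opening of the 15.2.1 sentence, or 15.4, will enter everything to day 28. A site that follows the rest of that sentence, or 9.3.4, need not. Nothing in the plan would show which rule a site applied.

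**Working it through.** The documents give no figure on this point, so there is none to reproduce. The check compares the rules and then asks how much of the window they leave exposed.

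**1. Which events fall in the gap.** Take an AE that starts after the last bemcentinib dose and within 28 days of it.

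| Event | Counted by SAP 5.8.1 | Recording required |
|---|---|---|
| Related, serious | yes | yes |
| Related, non-serious | yes | yes (9.3.4, 15.2.1) |
| Unrelated, serious | yes | yes (15.2.2) |
| Unrelated, non-serious | yes | not by the limit in 9.3.4, 15.2.1 and SAP 4.3.4 |

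Only the last row is exposed.

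**2. Which tables are exposed.** The all-cause tables (14.3.1.2.1.x and 14.3.1.2.2.x), the non-serious tables (14.3.1.7.x), the non-serious part of the Grade 3 or higher tables (14.3.1.5.1.x), and the 10% tables (14.3.1.6.x), where a term could drop below the threshold. The SAE tables are complete under 15.2.2. The related-AE tables count patients with a related event over the cohort total. Related events are still collected and the denominator is fixed, so those percentages do not move.

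**3. Unit of counting.** SAP 5.8.1 counts a patient once per event, at the worst grade. A table entry falls only if the unrecorded event was that patient's first of that term, or the highest grade of it.

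**4. Share of the window under restricted collection.** With T days from first to last dose, full 21-day cycles and a full 28 days of follow-up, the share is 28/(T + 28):

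- 1 cycle: 28/(21 + 28) = 57%
- 2 cycles: 28/(42 + 28) = 40%
- 3 cycles: 28/(63 + 28) = 31%
- 6 cycles: 28/(126 + 28) = 18%

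**5. Illustration only, in events rather than patients.** Assume a constant AE rate through the window, a share q of AEs that are related, a share s of unrelated AEs that are serious, and sites that record no more than they must. The unrecorded share is [28/(T + 28)] × (1 − q) × (1 − s). None of q, s or T comes from the documents.

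- T = 63, q = 0.3, s = 0.25: 0.308 × 0.70 × 0.75 = 0.16 unrecorded.
- T = 42, same q and s: 0.40 × 0.70 × 0.75 = 0.21 unrecorded.
- Low end, T = 252, q = 0.6, s = 0.5: 0.10 × 0.40 × 0.50 = 0.02.
- High end, T = 21, q = 0.2, s = 0.1: 0.571 × 0.80 × 0.90 = 0.41.

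A range of 2% to 41% shows that the result is driven by the assumptions. By step 3, these event figures do not carry over to the patient percentages in the SAP tables.

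**6. The two clocks.** The collection limit starts at the last dose of bemcentinib. The SAP window ends 28 days after the last dose of study drug, and SAP 5.8.1 does not say which drug. Protocol 9.3.2 lets cytarabine or decitabine continue alone in B2, B3 and B5. If the partner drug counts as study drug, the SAP window can run past the 28 days that 15.2.1 covers.

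**The case against.** The best defence is that the wording sets a minimum and forbids nothing. The opening of 15.2.1 and the duty in 15.4 call for all AEs, and the Final Study Visit (protocol 11.4) lists AE recording without restriction, so sites may well have entered everything. This stands as far as it goes: under-counting is likely if the limit is applied, but it is not certain.

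It can also be said that the serious events are safe and that the safety analysis is descriptive, with no statistical comparison of cohorts (SAP 5.1, 5.8). Both are true. They confine the problem to unrelated non-serious events. They do not remove it from tables that serve the Part B primary objective and that will be read side by side.

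A reader might infer that the plan overstates how much of the toxicity is related to bemcentinib. The documents do not support that as a statement about any planned output. The SAP plans no ratio of related AEs to all AEs, and related incidence is patients over the cohort total. A ratio would be too high only if someone formed it from the two sets of tables. In the overall summary by maximum relationship, a patient whose only AEs were unrelated, non-serious and after the last dose could be missing, but the count of patients with a related event is unchanged.

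Nor can 15.4 be read as a competing 28-day rule, since it names no window. The firmer internal conflict is within the 15.2.1 sentence itself.

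**Conclusion.** The mismatch is real, and nothing in either document resolves it. The all-cause TEAE window in SAP 5.8.1 is wider than the required collection for one class of event: unrelated, non-serious AEs that start after the last bemcentinib dose. The tables named above can under-count these, to an extent that may differ between sites and is relatively larger where treatment is short. SAE tables and patient-level related-AE incidence are sound.

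The text conflict is certain; its size is not. The only figures that do not depend on assumed event rates are the window shares of 57%, 40%, 31% and 18% after 1, 2, 3 and 6 cycles, and these rest on full cycles and a full 28 days of follow-up. They show exposure, not bias. The point should be corrected because the tables serve the primary objective of Part B and the correction is cheap.

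**What to change.** **For data already collected.** Protocol 16.8 records Parts A and B3 as complete and B2 enrolment as closed by 17 March 2020, so a new collection rule cannot recover those events. In SAP 5.8.1:

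- end the all-cause window for non-serious TEAEs at the last bemcentinib dose, naming that drug, because restricted collection starts there;
- tabulate related AEs and all SAEs from the following 28 days separately;
- state how AEs during continued cytarabine or decitabine alone are handled in B2, B3 and B5;
- note the limitation in the clinical study report.

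**For data still to be collected.** Reconcile protocol 9.3.4 and 15.2.1 and SAP 4.3.4 with the general duty in 15.4, so that all AEs are recorded to day 28. The Final Study Visit already takes place then and already lists AE recording.

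**Cost.** Changes of wording, one extra safety table, and some extra AE entries, which will include events due to the disease or to later therapy.

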15.2.2. Serious Adverse Events

Any SAE experienced by a patient between the time of the first administration of bemcentinib and 28 days after the last administration is to be recorded on an SAE Report Form as well as in the eCRF within 24 hours of knowledge by the investigator of its occurrence, regardless of the severity and causality of the event. The exception to this will be patients who experience an SAE due to a Screening assessment. Such events should also be reported and will be recorded in the CSR. SAEs with a suspected relationship with bemcentinib will be collected indefinitely. The SAE Report Form should be e-mailed to the [Syneos](mailto:[contact]) Health Safety and Pharmacovigilance Global Safety Mailbox [contact].

All SAEs that have not resolved by the end of the study, or that have not resolved upon the patient's discontinuation from the study, must be followed until any of the following occur:

- The event resolves
- The event stabilizes
- The event returns to baseline status
- The event can be attributed to agents other than the IMP or to factors unrelated to study conduct
- It becomes unlikely that any additional information can be obtained

Any event requiring hospitalization (or prolongation of hospitalization) that occurs during the course of a patient's participation in a clinical study must be reported as an SAE. Exclusions to this are hospitalizations:

- For pre-scheduled or routine elective procedures (as long as the qualifying condition did not worsen or progress, in the opinion of the investigator, since signing the ICF)
- For social reasons, in the absence of an AE e.g. for respite care
- Due to expected deterioration caused by disease progression

15.2.3. All Events

All events must be assessed to determine the following:

- If the event meets the criteria for an SAE as defined in Section 15.2.2
- The severity of the event as defined in Section 15.3.1
- The relationship to bemcentinib as defined in Section 15.3.2

15.3. Safety Classifications

15.3.1. Assessment of Severity

The investigator/designee will rate the severity of each AE according to CTCAE. For each sign or symptom, the maximum or highest grade observed since the last visit should be reported. If the symptom or event cannot be graded according to CTCAE, the following grade (severity) rating guideline will be used:

Grade 1	Mild	The AE is transient and easily tolerated by the subject
Grade 2	Moderate	The AE causes the subject discomfort and interrupts the subject's usual activities
Grade 3 or 4	Severe	The AE causes considerable interference with the subject's usual activities and may be incapacitating or life-threatening

15.3.2. Assessment of Causality

The investigator will assess the causality of the AE with respect to the IMP according to the following guidance:

Unrelated The Adverse Event is clearly unrelated to bemcentinib

Unlikely	The Adverse Event is doubtfully related to bemcentinib
Possible	The Adverse Event may be related to bemcentinib
Probable	The Adverse Event is likely to be related to bemcentinib
Definite	The Adverse Event is clearly related to bemcentinib

If in the opinion of the investigator an SAE is considered not related an alternate etiology must be provided. The causality assessment given by the investigator should not be downgraded by the sponsor. If the sponsor disagrees with the investigator's causality assessment, both the opinion of the investigator and the sponsor should be provided with the report.

15.3.3. Assessment of Expectedness

An unexpected adverse event is an event, the nature or severity of which is not consistent with the reference safety information (RSI) presented in the IB for the IMP. The responsibility for determining expectedness of an ADR falls to the sponsor.

15.3.4. Immediate Reporting of Serious Adverse Events

Expedited safety reporting within this clinical study complies with the ICH Guideline for Clinical Safety Data Management: Definitions and Standards for Expedited Reporting (E2A), investigational new drug (IND) application safety reporting (under 21CFR312.32), and with applicable local regulatory requirements.

The sponsor assumes responsibility for appropriate reporting of AEs to the Regulatory Authorities and main Research Ethics Committees (REC)/Institutional Review Boards (IRB). Although this responsibility can be delegated to the sponsor's Contract Research organization (CRO), the sponsor retains ultimate responsibility for safety reporting.

All SAEs that are unexpected and associated with the use of the IMP are classified as suspected unexpected serious adverse reactions (SUSARs) and must be reported to the main RECs/IRBs and Regulatory Authorities within 7 calendar days if fatal or life threatening, or within 15 calendar days if non-life threatening and non-fatal. The sponsor/designee must also report SUSARs to all investigational sites.

Any safety information from other observations that could change the risk-benefit evaluation of the IMP should be promptly communicated to the Regulatory Authorities and main RECs/IRBs. Any other SUSARs associated with the IMP should be reported as soon as the sponsor becomes aware of them including SUSARs which occur in another clinical study

conducted by the same sponsor or which are identified by spontaneous reports, a publication, or which are transmitted to the sponsor by another Regulatory Authority.

Other safety issues that also qualify for expedited reporting where they might materially alter the current benefit-risk assessment of the IMP (sufficient to consider changes in the administration or in the overall conduct of the trial), for instance include:

- An increase in the rate of occurrence of an expected serious adverse reaction, which is judged to be clinically important
- Post-study SUSARs that occur after the patient has completed a clinical trial and are reported by the investigator to the sponsor
- New events relating to the conduct of the trial or the development of the IMP likely to affect the safety of the patients, such as:
 - An SAE which could be associated with the trial procedures and which could modify the conduct of the trial
 - A major safety finding (such as carcinogenicity, which differs to the underlying disease)

Expedited reporting is not usually required for reactions which are serious but expected, and it is inappropriate to report events that are considered unrelated to the IMP.

